6.7. Accountability of Test Articles

JJVC will provide the Investigator with sufficient quantities of study articles and supplies to complete the investigation. The Investigator is asked to retain all lens shipment documentation for the test article accountability records.

Test article must be kept in a locked storage cabinet, accessible only to those assigned by the Investigator for dispensing. The Investigator may delegate this activity to authorised study site personnel listed on the Site Delegation Log. All test articles must be accounted.

Following final reconciliation of test articles by the monitor, the Investigator will destroy both used and unused lenses per local guidelines and in accordance with sponsor policy.

If there is a discrepancy between the shipment documents and the contents, contact the study monitor immediately.

[REDACTED]

7. STUDY EVALUATIONS

7.1. Time and Event Schedule

Table 3: Time and Events

Procedure	Screening	Baseline	Assessment 1	Assessment 2	Exit
Informed consent	✓	-	-	-	-
Eligibility screening	✓	-	-	-	-
Subject demographics	✓	-	-	-	-
General health and medication history and concomitant medications	✓	-	-	-	-
Subject's own contact lens information	✓	-	-	-	-
Habitual lenses	✓	-	-	-	-
Sphero-cylindrical refraction and visual acuity (VA)	-	✓	-	-	✓
Best vision sphere and monocular VA	-	✓	-	-	-
Ocular topography	-	✓	-	-	-
Slit lamp biomicroscopy	-	✓	-	-	✓
Lens information and any modification	-	-	✓	✓	-
Distance spherical over-refraction and monocular VA	-	-	✓	✓	-
Subjective ratings - comfort on insertion and settling and handling	-	-	✓	✓	-
Subjective Vision Quality	-	-	✓	✓	-
Lens fit assessments	-	-	✓	✓	-

7.2. Detailed Study Procedures

Subject should enter the study in habitual contact lenses or spectacles.

VISIT 1

Screening			
Step	Procedure	Details	
1.1	Statement of Informed Consent	Each subject must read, understand, and sign the Statement of Informed Consent before being enrolled into the study. The Principal Investigator or his/her designee conducting the informed consent discussion must also	

		sign the consent form. Note: The subject must be provided a signed copy of this document.	
1.2	Demographics	Record the subject's date of birth, gender, race and ethnicity.	
1.3	Medical History and Concomitant Medications	Questions regarding the subjects' medical history and concomitant medications.	
1.4	Habitual Lenses	Questions regarding the subject's habitual lens type and parameters.	
1.5	Eligibility after Screening	All responses to Screening Inclusion Criteria questions must be answered "yes" and all responses to Exclusion Criteria must be answered "no" for the subject to be considered eligible.	
Baseline			
Step	Procedure	Details	
1.6	Subjective Refraction	The investigator will complete a subjective refraction (sphere and cylinder) and record the resultant high contrast distance monocular visual acuity to the nearest letter. Also, complete best vision sphere (BVS) and the resultant high and low contrast distance monocular visual acuity to the nearest letter. Best corrected high contrast distance visual acuity (BVA) must be 0.20 logMAR or better in each eye.	
1.7	Biometry measurements	Record the baseline Biometry measurements: – Corneal topography: Sim-K-readings and corneal shape factor, – Horizontal HVID – Horizontal & vertical corneal diameter, corneal sagittal height, corneo-scleral junction angle (Anterior OCT).	Topography Measurement using MEMONT E300 Corneal Topographer Measuring ocular Topography by VISANTE OCT
1.8	Slit Lamp Findings	A slit lamp examination will be used to determine eligibility. The following findings will be graded:	Appendix D

		
 i. Limbal hyperaemia ii. Bulbar hyperaemia iii. Tarsal abnormalities iv. Corneal staining v. Conjunctival staining vi. Other significant findings 
If any of these slit lamp findings are higher than grade 2, the subject is ineligible to continue but may return at a later date to complete another Baseline. If after a total of two attempts the subject is deemed ineligible, then complete the Final Evaluation.
	
1.9	Eye Rinse	The study coordinator, investigator, or technician will rinse the subject's eyes thoroughly with saline.	
1.10	Baseline Eligibility	All responses to Baseline Inclusion Criteria questions must be answered "yes" and all responses to Exclusion Criteria must be answered "no" for the subject to be considered eligible.	

Assessment 1: Lens Pair 1			
Step	Procedure	Details	[REDACTED]
1.11	Randomisation	Chose the study lens based on the Lens Fitting schedule	
1.12	Lens Fitting	
The lens powers will be based on the vertex-corrected (12mm), best vision sphere subjective refraction. Record the parameters of the lenses on the (lens type / lot number, lens powers).
 
The subject will insert the lenses. Check for any lens damage and replace if necessary.
	
1.13	Subjective Ratings	Record handling and initial comfort.	Appendix D
1.14	Time Interval	Please wait for at least 30-45 minutes from final lens insertion to continue.	
1.15	Subjective Ratings	Ask subjects to grade comfort of the lenses.	Appendix D
1.16	Spherical Over-refraction	Perform a spherical over-refraction OD and OS.	
1.17	Visual Acuity	Record the high and low contrast distance monocular visual acuity with the contact lenses to the nearest letter. Smaller lines must be shown until the subject incorrectly	Appendix D

		identifies at least 50% of the letters.	
1.18	Vision Quality	Record subjective vision quality.	Appendix D
1.19	Lens Fit Assessment	Record the following lens fit characteristics using VCR assessment system: * i. Horizontal & vertical centration ii. Corneal coverage iii. Post-blink movement in primary gaze and up-gaze iv. Version lag v. Edge tightness vi. Tightness (push-up) vii. Diameter acceptance viii. Overall fit acceptability * This provides more precise fit assessments of fit than those used in routing studies	Appendix D
1.20	Lenses	Remove and discard lenses	

Assessment 2: Lens Pair 2			
Step	Procedure	Details	█
As per Lens Pair 1			

FINAL EVALUATION

The final evaluation will ordinarily take place immediately following Lens Pair 2. It may also take place at any point the subject discontinues the study or is terminated from the study.

Final Evaluation			
Step	Procedure	Details	█
F.1	Final Exam Form	Indicate if the subject completed the study successfully. If subject discontinued from the study indicate the reason.	
F.2	Subjective spherocylindrical Refraction	Complete a subjective refraction (sphere and cylinder) and record the resultant high contrast distance monocular visual acuity to the nearest letter.	█

F.3	Exit Slit Lamp Biomicroscopy	The following findings will be graded: i. Limbal hyperaemia ii. Bulbar hyperaemia iii. Tarsal abnormalities iv. Corneal staining v. Conjunctival staining vi. Other significant findings	[REDACTED]
-----	---------------------------------	--	------------

7.3. Unscheduled Visits

If, during the investigation, a subject requires an unscheduled visit to the clinical site, the following information will be collected at a minimum:

- Chief complaint prompting the visit. If the reason is an adverse event, the applicable eCRF for the adverse event must be completed and subject record completed as appropriate
- Date and time of the visit and all procedures completed at the unscheduled visit
- Review of adverse event and concomitant medications
- Documentation of any test article dispensed or collected from the subject, if applicable
- Slit lamp findings (using the Slit Lamp Classification Scale)

If the Investigator withdraws a subject from the study, the final study visit case report forms must be completed indicating the reason(s) why the subject was withdrawn. The subject record must be completed documenting the date and primary reason for withdrawal and the study CRA notified.

Any ocular and non-ocular Adverse Events that are ongoing at the time of the study visit will be followed by the Investigator, within licensure, until they have resolved, returned to pre-treatment status, stabilised, or been satisfactorily explained. If further treatment i.e., beyond licensure is required, the subject will be referred to the appropriate health care provider.

The following information will be collected during an unscheduled visit.

Step	Procedure	Details	[REDACTED]
U.1	Chief Complaints	Record the subject's chief complaints for reasons for the unscheduled visit	[REDACTED]
U.2	Change of Medical History and Concomitant Medications	Questions regarding the change of subjects' medical history and concomitant medications.	[REDACTED]
U.3	Entrance VA	Record the entrance distance visual acuity (OD, OS and OU) to the nearest letter.	[REDACTED]
U.4	Subjective Sphero-cylindrical Refraction	Perform bare-eye subjective sphero-cylindrical refraction with a phoropter (adopt the maximum plus to maximum visual acuity (MPMVA) approach and use the duo-chrome test for binocular balancing) and record the best corrected	[REDACTED]

Step	Procedure	Details	
		distance visual acuity to the nearest letter (OD, OS, OU).	
U.5	Slit Lamp Biomicroscopy	FDA Slit Lamp Classification Scale will be used to grade the findings. If no slit lamp finding is noted on the EDC form it is considered as a zero "0" grade for all observations listed. After the slit lamp examination, at the discretion of the Investigator, rinse the subject's eyes thoroughly with preservative-free saline.	
U.6	Exit Visual Acuity	Record the subject's exit distance visual acuity (OD, OS and OU) to the nearest letter with the subjects wearing the study provided spectacle glasses.	

7.4. Laboratory Procedures

Not Applicable

8. SUBJECTS COMPLETION/WITHDRAWAL

8.1. Completion Criteria

Subjects are considered to have completed the study if they:

- Provided informed consent;
- They are eligible;
- Clinical assessments were completed with all three study contact lenses.

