1.1. Name and Descriptions of Investigational Products

This study will compare two daily disposable lens designs in two different materials: ACUVUE OASYS[®] 1·Day (senofilcon A), 1·Day ACUVUE[®] TruEye[®] (narafilecon A).

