4. STUDY DESIGN AND RATIONALE

4.1. Description of Study Design

This will be a one-day, double-masked, randomised, repeated measures, and non-dispensing cross-over study. Each subject will wear the steeper base curve of each design in one eye while the flatter base curve of each will be worn in the other. The two base curves of a given lens type will be worn simultaneously (i.e. contralaterally). A total of four lenses will therefore be worn by each subject (2 per eye).

Lenses will be evaluated after 30-45 minutes settling. There will be no washout period between study lenses.

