4.3. Enrolment Target and Study Duration

Approximately 45-60 subjects will be enrolled across two sites (15-30 subjects per site) to ensure that at least 43 subjects will complete the study. Enrolled subjects will be habitual wearers of spherical contact lenses. All subjects will be between 18 and 55 years of age. Subjects will be considered enrolled after signing the informed consent. Subjects will wear the Test and Control contact lenses for approximately 45 minutes each for a total study duration of approximately 3 hours per subject.

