5. TEST ARTICLE ALLOCATION AND MASKING

5.1. Test Article Allocation

This will be a one-day, double-masked, randomised, repeated measures study. Each subject will wear three pairs of lenses each in two base curves. The order of the Test and Control lenses worn and the assignment of the steeper BC to right or left eyes will be randomised.

The randomisation scheme was created using a random number generating computer program (SAS version 9.4 or higher, SAS Institute, Cary, NC) with a blocking system of four subjects stratified by site. Each subject will be randomly assigned to wear one of two lens sequences with the steeper base curve randomly assigned to the left or right eye giving a total of four potential sequences:

- i. T/C steeper lens in right eye
- ii. T/C steeper lens in left eye
- iii. C/T steeper lens in right eye
- iv. C/T steeper lens in left eye

The study site must follow the randomisation scheme provided and complete enrolment according to the randomisation list and not pre-select or assign subjects. The randomised assignment of subjects will be performed prior to the first fitting. The following must have occurred prior to randomisation:

- Informed consent has been obtained
- Subject meets all the inclusion / exclusion criteria
- Subject history and baseline information has been collected

Randomly-permuted block randomisation will be used to avoid bias in the assignment of subjects to treatment, and to enhance the validity of statistical comparisons across treatment groups.

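### Do the references to a third lens in the completion criterion (8.1) and the allocation text (5.1) leave the trial without a workable definition of a completer?

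*Combined protocol and SAP*

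**What the plan says.** Two sentences in the protocol count three lenses. The last condition in 8.1 (Completion Criteria) reads "Clinical assessments were completed with all three study contact lenses". The first paragraph of 5.1 (Test Article Allocation) reads "Each subject will wear three pairs of lenses each in two base curves".

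The rest of the design text counts two types:

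- Section 1.1: "This study will compare two daily disposable lens designs in two different materials".
- Section 4.1, repeated in the synopsis: "A total of four lenses will therefore be worn by each subject (2 per eye". The synopsis also gives the number of periods as two.
- Section 5.1, second paragraph: "Each subject will be randomly assigned to wear one of two lens sequences". The four sequences listed beneath contain only T and C.
- Section 6.1, Table 1: one Test column and one Control column.
- Section 7.1, Table 3: Assessments 1 and 2 only.
- Section 7.2: "The final evaluation will ordinarily take place immediately following Lens Pair 2".

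The number of completers appears in 4.3, where enrolment is set "to ensure that at least 43 subjects will complete the study". At exit, step F.1 in 7.2 tells the site: "Indicate if the subject completed the study successfully".

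**The concern.** Section 8.1 is the only place where the protocol says explicitly what makes a subject a completer. If completion needs assessments with three lenses and the schedule supplies two pairs, a subject who follows the protocol perfectly still fails the criterion. Taken at face value, the completer count would be zero whatever the recruitment, the target of 43 could never be reached, and every exit form would have to record a non-completer.

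The sentence in 5.1 adds to the worry because it stands in the section that governs allocation. It implies six lenses per subject, whereas 4.1 gives four. Table 1 also describes the stock as 30 x 6 items, which could be a third trace of the same count. If a third lens were really intended, the randomisation, the schedule and the analysis models would all be incomplete.

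**Working it through.** The question is whether three can be the intended number anywhere, and whether any decision or analysis depends on it.

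**Lenses per subject.** Lens types x eyes = 2 x 2 = 4. This reproduces the total in 4.1 and the synopsis. Three pairs would give 3 x 2 = 6.

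**Randomised sequences.** Lens orders x eye assignments = 2 x 2 = 4. This reproduces items i to iv in 5.1 and agrees with the block size of four stated there. With three lens types and all orders in use, the count would be 6 x 2 = 12.

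**Labels.** Section 6.4 shows four sample labels (codes D, F, J and R), two at base curve 8.50 and two at 9.00. That is 2 types x 2 base curves = 4.

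**Stock remark in Table 1.** In 0.25 D steps, -6.00 to -1.00 D gives 21 powers and +2.00 to +4.00 D gives 9, so 21 + 9 = 30. This reproduces the 30. Two types x two base curves gives 30 x 4 = 120 items; the table's 30 x 6 is 180. The difference is 60 = 30 x 2, which would fit one further lens type in two base curves. The protocol does not say what the 6 counts, so this reading is an assumption.

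**What 8.1 counts.**

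| Unit | Number in the design | Number in 8.1 |
|---|---|---|
| Lens types | 2 | 3 |
| Pairs (assessments) | 2 | 3 |
| Lenses | 4 | 3 |

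Three matches no unit. There is therefore no competing reading of the design. The only one consistent with the schedule is that both lens types were assessed.

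**What depends on 8.1.**

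- *Per-protocol population (14.3).* It requires all assessments to be completed without a substantial deviation. It does not refer to 8.1, and Table 3 lists two assessments.
- *Safety population (14.3).* It requires use of any test article and at least one recorded observation. Completion plays no part.
- *Sensitivity analysis trigger (14.5).* It compares the analysis and safety populations against a 15% threshold, and neither population uses 8.1.
- *Replacement of subjects (synopsis, 8.2).* It is triggered by premature discontinuation. The withdrawal reasons in 8.2 do not include a missing third lens.
- *Models and intervals (14.5, 14.6).* Every contrast is Test against Control by base curve. No third level of lens type appears.
- *Target of 43 (4.3) and step F.1 (7.2).* Both use the idea of completing the study, and neither cites 8.1.

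Replacing three by two in 8.1 and 5.1 would change none of these.

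**The case for a change.** The best argument for acting is that the error is certain, sits in current and unredacted text, and costs almost nothing to correct. It affects the only explicit completion definition and the opening of the allocation section, and perhaps the stock count in Table 1 as well. That suggests a common source rather than one mistyped word. An operative definition that nobody can satisfy does not belong in an approved protocol.

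Most of the factual part stands. Sections 8.1 and 5.1 are wrong as written, 5.1 contradicts itself, and the Table 1 count does not agree with two types in two base curves. It would be reasonable to tidy these words if the protocol were reissued for another reason.

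What does not stand is the step from wrong wording to a consequence. A site cannot act on the error, because the randomisation list contains only Test and Control and the visit ends after the second pair. No realistic course of events would have a subject with both pairs assessed recorded as a non-completer. The link from 8.1 to the target of 43 and to F.1 is a plausible inference, but the protocol does not make it. The stock remark concerns supply and has no bearing on completion, allocation or analysis.

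**Conclusion.** The inconsistency is genuine and clerical. The design is a two-type, two-pair, four-lens crossover, and the lens total, the sequences, the labels, the table columns and the schedule all agree on it. The criterion in 8.1 will be applied as completion of both assessments, the only reading that the schedule allows. Under that reading the target of 43 is attainable as written.

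The size of the effect on the analysis populations, the primary and secondary estimates, their confidence intervals and the non-inferiority conclusions is zero. The conclusion rests on two assumptions: that no third lens is hidden in redacted text, which the two-column Table 1 and the T/C and C/T sequences make very unlikely, and that the per-protocol population is built from 14.3 as written. Correcting the wording would alter neither what the trial does nor what it can conclude, so no change to the plan is called for.

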8.2. Withdrawal/Discontinuation from the Study

A subject will be withdrawn from the study for any of the following reasons:

- Subject death during the study period
- Subject withdrawal of consent
- Subject not compliant to protocol
- Subject lost to follow-up
- Subject no longer meets eligibility criteria (e.g. the subject becomes pregnant)
- Subject develops significant or serious adverse events causing discontinuation of study lens wear
- Subjects who have experienced a Corneal Infiltrative Event (CIE)
- Investigator's clinical judgment regarding the subject safety reasons (that it is in the best interest of the subject to stop treatment)

For discontinued subjects, the Investigator will:

- Complete the current visit (scheduled or unscheduled)

- Complete the Final Evaluation, indicating the reason that the subject was discontinued from the study
- Record the spherocylindrical refraction with best corrected distance visual acuity
- Collect used test article(s) (worn or brought to the visit) from the subject and discard them, unless otherwise stated in Section 7.2
- Collect all unused test article(s) from the subject

An additional subject may be enrolled if a subject discontinues from the study prematurely.

In cases where a subject is lost to follow-up, every possible effort must be made to contact the subject and determine the reason for discontinuation/withdrawal. The measures taken to follow up must be documented including two written attempts and a certified letter (or equivalent) as the final attempt.

9. PRE-STUDY AND CONCOMITANT INTERVENTION/MEDICATION

Concomitant medications will be documented during screening and updated during the study. Disallowed medications for this study include: use of medications that contraindicate contact lens wear.

Concomitant therapies that are disallowed include: therapies in which contact lens wear is contraindicated.

10. DEVIATIONS FROM THE PROTOCOL

Investigator will notify study sponsor upon identification of a protocol deviation. Major protocol deviations must be reported to the sponsor within 24 hours after discovery of the protocol deviation. The Investigator will report deviations per IRB/IEC requirements. All deviations will be tracked and corrective actions implemented as appropriate.

If it becomes necessary for the Investigator to implement a deviation in order to eliminate an immediate hazard to the trial subject, the Investigator may implement the deviation immediately without notification to the sponsor. Within 24 hours after the implemented deviation, the Investigator must notify and provide the rationale to the Sponsor and, as required, the IEC/IRB.

11. STUDY TERMINATION

The occurrence of one or more Unanticipated Serious Adverse Device Effect (USADE), or any SAE where the relationship to study agent cannot be ruled out, may result in stopping further dispensing of test article. In the event of a USADE or SAE, the Sponsor may unmask the treatment regimen for the subject(s) and will discuss this with the Investigator before any further subjects are enrolled.

The Sponsor will determine when a study will be stopped. The Principal Investigator always has the discretion to initiate stopping the study based on patient safety or if information indicates the study's results are compromised.

JJVC reserves the right to terminate the study at any time for any reason. Additionally, the IEC/IRB reserves the right to terminate the study if an unreasonable risk is determined. The study can be terminated by the Principal Investigator at the individual clinical site due to specific clinical observations, if in their opinion, after a discussion with JJVC, it is determined that it would be unwise to continue at the clinical site.

JJVC (and the IEC/IRB and DMC, if applicable) will evaluate all adverse events. If it is determined that an adverse event presents an unreasonable risk, the investigation, or that part of the investigation presenting the risk, will be terminated, as soon as possible.

Should the study be terminated (either prematurely or as scheduled), the Investigator will notify the IEC/IRB and Regulatory Authority as required by local regulatory requirements.

